23.0 Alternative Methods or Treatments

23.1 * Describe alternative methods or treatments for the disease(s) under study, if any, that were considered and why they will not be used:

There is always the option not to participate in this study.

24.0 Data and Safety Monitoring

This section describes the Data and Safety Monitoring Plan (DSMP) required of each protocol undertaken at the CCTS according to HRPP and NIH policies Notice 98 -084 and Notice 00-038, as cited in Help Sections below. Depending on the level or risk and trial phase, some protocols will need Data and Safety Monitoring Boards.

24.1 * Overall Risk Classification

An estimate of risk is necessary to evaluate the adequacy of the planned monitoring. The HELP section provides guidance in making the risk assessment.

Read the risk definitions and examples of risk in the HELP section and select the risk category that best describes the current study.

If your assessment differs from the definitions the HELP section, describe any factors that modify your judgment of the overall risk in the text box after the risk designation.

- MINIMAL RISK
- LOW RISK
- MODERATE RISK
- SIGNIFICANT RISK

Please provide any optional description(s):

24.2 Protocols Involving Minors

The chance of direct benefit to the child, or to understanding a disorder not otherwise understood, may be major factors in justifying more than minimal risk in research involving children.

Based on the above definitions, please specify your study's risk classification below:

- NOT GREATER THAN MINIMAL RISK (the risk of daily life to a healthy child living in a safe environment) 45 CFR 46.404
- GREATER THAN MINIMAL RISK WITH DIRECT BENEFIT TO SUBJECT; 45 CFR 46.405
- GREATER THAN MINIMAL RISK, NO DIRECT BENEFIT, BUT BENEFIT TO UNDERSTANDING OF SUBJECT'S DISORDER; 45 CFR 46.406
- RESEARCH NOT OTHERWISE APPROVED PRESENTING OPPORTUNITY TO UNDERSTAND, PREVENT OR ALLEVIATE SERIOUS PROBLEM AFFECTING CHILDREN 45 CFR 46.407 (cannot be approved by IRB; requires public comment)

24.3 DSMB

1. The NIH requires that all SIGNIFICANT RISK protocols have a **Data and Safety Monitoring Board** and provide information about the expertise and independence of that Board
2. Phase III trials require a Data and Safety Monitoring Board,
3. A DSMB may be appropriate for some Phase I and II protocols. (See Help for examples.)
4. It is the investigator's responsibility to report to the IRB, the findings and recommendations of the DSMB as they become available.

Please specify:

- A DSMB is required for this study
- A DSMB is not required for this study
- Unsure

If a DSMB is required, please indicate why:

- Significant Risk
- Study Design - Phase III
- Study Design - Placebo Controlled
- Study Design - Multicenter Trial
- Study Design - Other Factor

If other factor, please specify:

If a DSMB is required, select one:

- An independent DSMB has been constituted; the members, mission charter, schedule for meetings, and a listing of the data to be reviewed by the DSMB will be attached.
- A DSMB has not yet been constituted; the PI will consult the IRB and/or CRSO for assistance in assembling a DSMB.

If a DSMB is not required, but is being constituted for other reasons, please explain:

24.4 * Safety Review

Select one:

- Safety Review is conducted as follows: Laboratory results for research volunteers will be reviewed in a timely manner, usually within 24 hours of receipt by a licensed practitioner. The potential clinical significance of any abnormal finding will be documented in the medical and research record(s), and an appropriate plan or referral developed. The PI's review of safety issues at research team rounds will be documented in the meeting minutes.
- Protocol Specific

If Protocol Specific, please describe safety review for protocol tests and procedures that require other than routine review. For example, an EKG taken to detect emerging conduction problems might require immediate safety review.

24.5 Monitoring

Monitoring Personnel: See Help Bubble to the right.

Internal Monitoring

The PI or his/her designee shall conduct internal monitoring to assure the safe and proper conduct of the protocol and all the elements listed above in monitoring, following the general principles of quality management. The intensity and frequency of internal monitoring will depend on the protocol risk to subjects, the experience of the PI and research team, rate of enrollment, and specific details of the protocol.

Internal monitoring of informed consent and eligibility documentation will be conducted by the research team shortly after enrollment begins. Internal monitoring activities will be documented by logs, meeting minutes or other systematic means.

Specify the research team members who will conduct the internal monitoring of the study (see Help for who may monitor):

For new investigators: Internal monitoring should be conducted at least monthly by new investigators until there are essentially no findings to correct at each review.

External Monitoring

* Is external monitoring planned for this protocol?

- Yes
- No
- Unsure

If external monitoring is planned, please specify (see Help for who may monitor):

- (Significant Risk) External monitoring will occur at least every six weeks unless there is no enrollment
- (Moderate Risk) External monitoring will occur at least quarterly
- (Low or Minimal Risk) External monitoring will occur at least annually

If external monitoring is planned, please specify the name of the monitor:

Note that copies of external monitoring reports must be supplied to the IRB and the CRSO as soon as they are made available

Additionally, audits of the research records of minimal, moderate or significant-risk protocols may be performed by the CRSO staff on a random basis or as part of a prospectively identified auditing plan.

24.6 Adverse Event Classification

Adverse events are classified by definition, severity, and association with the investigational trial.

Definition of an Adverse Event

Any unfavorable or unintended sign (including abnormal lab findings), symptom or disease temporally associated with the use of a medical treatment or procedure, or protocol, regardless of whether it is considered related to the medical treatment or procedure or protocol.

Definition of a Serious Adverse Event

Any unanticipated event that involves the following:

- results in death
- is life-threatening
- requires hospitalization or prolongs existing hospitalization
- results in persistent or significant disability/incapacity
- is any medical event which requires treatment to prevent one of the outcomes listed above

Other events can be classified as "serious adverse events" at the discretion of the PI.

Definition of Anticipated/Expected Adverse Event

Any adverse event, which has been reported in the Investigator's Brochure, package insert, safety reports, clinical protocol, consent form or listed in the NCI agent-specific Expected Adverse Event List³, is classified as an expected adverse event. The investigator must provide the available data of known adverse events and toxicities that have been associated with the study drug, device, intervention, or procedures. This information helps to define the level of risk of the trial and enables safety monitoring. A minimal risk trial may not have any defined risks and a statement to that effect is sufficient to meet the DSMP requirements.

Definition of an Unanticipated/Unexpected Adverse Event

Any adverse event that is not consistent with the known, predicted possible effects of the research protocol. An unexpected adverse event varies in nature, intensity or frequency from information on the investigational product provided in the Investigator's Brochure, package insert, safety reports, clinical protocol, or listed in the consent form.

Definition of an Unanticipated Problem (UaP)

A UaP is an event or circumstance that meets all the following three criteria: [1] the nature, severity, frequency of the event(s) or information was not expected in the descriptions in the study documents or the characteristics of the subject population being studied; [2] there is a reasonable possibility that the procedures involved in the research caused or are linked in a significant way to the problem; [3] the event or information suggests that the research places subjects or others at a greater risk of harm than was previously known or recognized (including physical, psychological, economic, or social harm).

Grade and Relatedness of Adverse Events:

Adverse Events are graded for severity and scored for relatedness to the protocol, according to a published scale. Several standardized AE Reporting scales are available. (See Help for links to these scales.)

* Please indicate the scale you intend to use:

- CTC v2.0 (<http://ctep.info.nih.gov/reporting/ctc.html>)
- CTCAE v3.0 (http://ctep.info.nih.gov/protocolDevelopment/electronic_applications/docs/ctcaev3.pdf)
- CTCAE v4.0 (http://evs.nci.nih.gov/ftp1/CTCAE/CTCAE_4.03_2010-06-14_QuickReference_8.5x11.pdf)

- AIDS Clinical Trials Group (<http://aactg.s-3.com/>)
- Other

If Other, please specify:

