21.0 Potential Risks to Subjects

21.1

* Describe any potential risks: physical, psychological, social, legal or other and assess their likelihood and seriousness. Indicate risks both to the subjects and to the embryo or fetus if the subject is or may become pregnant. Please provide the potential risks below:

Potential Risks associated with ingestion of Celecoxib are MI, CVA, hypertension, heart failure, renal failure, GI bleeding, ulcers, anemia, life-threatening skin reactions, life-threatening allergic reactions, liver disease including liver failure, and asthma attacks in people who have asthma. Other side effects include abdominal pain, constipation, diarrhea, flatus, heartburn, nausea, vomiting, and dizziness.

A metaanalysis of 9 studies that compared Celecoxib with other (over the counter) NSAID showed that serious upper gastrointestinal events occurred at a rate 45% less (18).

A nationwide review of cardiovascular risks for Cox-2 inhibitors revealed no significant risk of myocardial infarction, ischemic stroke or atrial fibrillation for Celecoxib (19)

Potential risks associated with venipuncture include discomfort or pain, ecchymosis, bleeding, phlebitis and infection at the needle insertion site. Additional risks include lightheadedness and a vasovagal response.

Potential risks associated with a fat biopsy include a vaso-vagal response and inflammation, discomfort, pain, bleeding, and a superficial infection at the site. A permanent scar with possible depression will develop at the biopsy site.

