22.0 Procedures to Minimize Risks

22.1 * Describe the procedures for protecting against or minimizing any potential risks, and include an assessment of their likely effectiveness. Include a discussion of confidentiality safeguards, where relevant, and arrangements for providing medical treatment, if needed.

Fat Biopsy:

Risks of the fat biopsy will be avoided by having only trained and qualified staff performing the procedure. Subjects will be instructed about signs and symptoms of infection, be given written instructions of wound care and removal of the butterfly dressing, and be provided with the investigator's contact information to call if necessary. A study team member will telephone each subject after discharge to monitor for complications.

Venipuncture:

To protect subjects from risks associated with venipuncture, only trained, skilled staff will perform this procedure.

Celecoxib:

All subjects will be carefully screened according to inclusion/exclusion criteria and judgment of the PI and nurse practitioner. Subjects will be carefully monitored, especially for cardiovascular and GI adverse events throughout the duration of their inpatient stay and will not be receiving Celecoxib after discharge.

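### The serious adverse event definition is limited to unanticipated events, so a serious event already listed as a celecoxib risk can miss expedited IRB reporting

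*Combined protocol and SAP*

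**What the plan says.** Section 24.6 opens its SAE definition with "Any unanticipated event that involves the following" and then lists death, threat to life, hospitalization, lasting disability, and events needing treatment to prevent one of these. Other events may be added "at the discretion of the PI".

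The same section defines an expected event by where it has already been reported. The sources include the "package insert, safety reports, clinical protocol, consent form". On the other side, "An unexpected adverse event varies in nature, intensity or frequency from information on the investigational product". An unanticipated problem must meet three criteria, the first being that "the nature, severity, frequency of the event(s) or information was not expected in the descriptions in the study documents".

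Section 21.1 gives the known risks: "Potential Risks associated with ingestion of Celecoxib are MI, CVA, hypertension, heart failure, renal failure, GI bleeding, ulcers", and further on "life-threatening skin reactions, life-threatening allergic reactions, liver disease including liver failure". Section 22.1 says that subjects will be "carefully monitored, especially for cardiovascular and GI adverse events" during the inpatient stay.

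Sections 24.7 and 24.8 set the reporting times to the IRB:
- SAEs: two working days, in line with a policy that is not reproduced.
- Unanticipated adverse events that are related and more than moderate in severity: two working days.
- Unanticipated problems: five working days.
- All adverse events: at least once a year.

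**The concern.** Seriousness is a matter of outcome; expectedness is a matter of whether the event is already on a list. Section 24.7 treats them as two axes, with one heading for serious events and another for unanticipated ones. The SAE definition in 24.6 merges them by making lack of anticipation a condition of being serious.

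The events most likely to be serious under celecoxib are those the protocol itself lists and monitors for. If being listed takes them out of the SAE class, whether the IRB hears of a hospitalized GI bleed within days depends on a judgement about expectedness or on the PI's choice, not on what happened to the subject. Speed of reporting is at stake, and so is any SAE tally drawn from these definitions.

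**Working it through.** There is no plan figure to reproduce. The check applies the definitions to the listed risks and follows each reporting route.

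**Step 1. Which serious events are listed?** From section 21.1 I count myocardial infarction, stroke, heart failure, renal failure, GI bleeding, life-threatening skin reactions, life-threatening allergic reactions and liver failure: 8 types, of which 2 are described as life-threatening in the listing itself. The count is a selection. Ulcers, anemia and asthma attacks are also listed and can be serious, and a GI bleed need not be. The argument needs only one such event.

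**Step 2. Are they expected under 24.6?** Yes. The clinical protocol is one of the named sources, and these events are reported in it.

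**Step 3. Follow a test case.** Take a GI bleed that leads to hospitalization and is consistent with the listing.

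| Route to the IRB | Time | Condition | Met? |
|---|---|---|---|
| SAE by definition (24.6, 24.7) | 2 working days | Unanticipated and serious outcome | No: anticipated |
| Unanticipated adverse event (24.6, 24.7) | 2 working days | Unanticipated, related, more than moderate | No: anticipated |
| Unanticipated problem (24.6, 24.8) | 5 working days | Not expected, plus two further criteria | No: first criterion fails |
| SAE by PI decision (24.6) | 2 working days | PI chooses to classify it so | Possible, not required |
| All adverse events (24.7) | At least annually | None | Yes |

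All 3 of the 3 expedited routes carry an expectedness test.

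**Step 4. When does a listed event still qualify?** There are two ways: the PI uses the discretion clause, or the event is judged to vary in nature, intensity or frequency from the product information. The second could be argued for myocardial infarction or stroke, since section 21.1 also cites a review that found no significant risk of them with celecoxib. On nature and intensity it is harder to argue for the two types listed as life-threatening, because a life-threatening case is what the listing describes.

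**Step 5. Exposure.** Section 12.7 plans 10 subjects dosed for 10 ± 1 days: 10 × 9 = 90 to 10 × 11 = 110 person-days. For the next year, section 13.9 projects 0 new consents and section 14.1 projects 0 inpatient days.

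**The case against.** The strongest reply is that the consequence is uncertain. SAE reporting follows a policy that is not in the documents and may already cover expected serious events. That stands, and it is why the delay can only be given as a range. If the policy is broader, though, the protocol's definition conflicts with it and still needs correcting.

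Second, the exception for unexpected events is wide. It includes frequency, and one case among 10 subjects is an observed 1/10 = 10%, which an investigator could call a departure from the known rate. The documents give no label rates, so this cannot be settled. The exclusion criteria in 13.12 also remove women with cardiovascular disease, peptic ulcer, bleeding disorders, drug hypersensitivity and asthma, so a listed event might be called unexpected in those enrolled. This is fair, but it leaves prompt reporting dependent on an expectedness judgement, which is the fault described.

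Third, the tick marks in 24.7 were lost in text extraction, so it is not known which optional routes were selected. If the unanticipated-event route to the IRB was not selected, there are two expedited routes rather than three. A sponsor or FDA route for SAEs would rest on the same definition, so it would not by itself catch a listed event. Section 24.5 sends external monitoring reports to the IRB if such monitoring is planned, but that selection is also lost and the route sets no event-level deadline.

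Finally, the wording looks like institutional form text, subjects are inpatients under observation, and little or no dosing remains. All of this lowers the practical effect. It does not change the fact that this is the only SAE definition in the protocol, and it also governs how events already recorded are classified.

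**Conclusion.** The concern holds on the protocol text. A serious event consistent with the celecoxib risks in 21.1 meets none of the three definitions that trigger expedited IRB reporting, and the only unconditional duty left is at-least-annual reporting. The two ways out, a judgement that the event differs from the listing and the PI's discretion, are both stated in 24.6, but neither makes reporting follow from outcome.

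The wording fault is certain; its consequence is not. The added delay runs from none, if the unseen policy already covers expected serious events, to as long as one year, if it does not. The conclusion assumes that anticipated in the SAE definition means the same as expected in the definitions that follow; 24.6 pairs the two terms in its own headings.

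The effect is confined to reporting time and SAE classification. Inpatient monitoring (22.1), the withdrawal criteria (25.1) and the paired analysis of urinary PGE-M are untouched. With 90 to 110 person-days of planned dosing and no further enrolment projected, this should be fixed but does not threaten the study's result.

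**What to change.** In 24.6, delete *unanticipated* from the SAE definition, so that an SAE is *any adverse event, whether or not anticipated,* that meets one of the listed outcomes. Keep expectedness as a separate classification, used for unanticipated adverse events and unanticipated problems. The two-working-day SAE clause in 24.7 can stay as it is; with the corrected definition it will cover listed serious events. Apply the corrected definition to events already recorded when SAEs are classified and reported.

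The cost is a one-line amendment and possibly a few more expedited reports in a 10-person study. If the institutional form does not allow that line to be edited, the same statement can be added as protocol-specific text.

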24.7 Reporting Adverse Events

All AEs will be reported to the IRB at least annually.

Reporting Serious AEs

Serious Adverse Events, (SAEs) will be reported to the IRB according to policy, within two working days of identification of the SAE.

Select all that apply:

SAEs will be reported to the Sponsor and or ESCROW

SAEs will be reported to the sponsor within how many days of the event?

SAEs will be reported directly to the FDA, per 21 CFR 312

SAEs must be reported directly to the FDA within 7 days of the event by the investigator/sponsor.

SAEs will be reported to another entity

Describe:

Reporting Unanticipated AEs:

Select all that apply:

UAEs will be reported to the IRB

UAEs that are related and greater than moderate severity must be reported to the IRB according to policy, within two working days of identification of the UAE.

UAEs will be reported to the Sponsor

UAE will be reported to the sponsor within how many days of the event?

UAEs will be reported to the FDA, per 21 CRF 312

UAEs will be reported to the FDA, per 21 CRF 312, within 15 days.

UAEs will be reported to another entity

Describe:

24.8 Reporting Unanticipated Problems

Unanticipated problems involving risks to subjects or others severe will be reported to the IRB and the CRSO within five working days.

24.9 CLIA/CLEP

Only laboratory and research tests that are CLIA/CLEP certified or waived may be used to determine eligibility, shared with research volunteers, and used in clinical decision making.

Select if applicable:

This study includes tests that are not CLIA/CLEP certified; the results of such tests will not be used in clinical decision making, or to determine eligibility, or shared with subjects or their health care providers.

24.10 Tissue Repository

Human Tissue and Data Repositories collect, store, and distribute human tissue materials and or data for research purposes. Repository activities involve three components: (i) the collectors of tissue samples\data; (ii) the repository storage and data management center; and (iii) the recipient investigators.

* Select one:

I DO NOT intend to collect, store, and distribute human tissue materials for research purposes
 I DO intend to collect, store, and distribute human tissue materials for research purposes, therefore this protocol entails the Operation of a Tissue Repository. The IRB requires that the protocol specify the conditions under which data and specimens may be accepted and shared, and ensuring adequate provisions to protect the privacy of subjects and maintain the confidentiality of data.

If you do intend to collect, store, and distribute human tissue materials, you will be asked to upload the following documents later on in the submission:

- A Sample collection protocol (for tissue collector collaborators to follow) and informed consent document for distribution to tissue collectors and their local IRBs.
- A Certificate of Confidentiality (to protect confidentiality of repository specimens and data).
- A Recipients Agreement describing the commitment of the recipient to preserve the anonymity of the samples shared.

25.0

Toxicity Management and Stopping Rules

25.1 * Describe any drug toxicity or other conditions under which the participation of a subject or the conduct of the study would be stopped in order to maximize safety (e.g., toxicity management and stopping rules):

Subjects may be withdrawn from the study if they meet the following criteria:
any evidence of a cardiac event

LFT 2X ULN
bilirubin 1.5-3.0 X ULN
creatinine 2 X ULN
PT/PTT > ULN
any evidence of bleeding

* Indicate withdrawal criteria and procedures below:

A subject will be withdrawn from the study if:
1) she is unable to tolerate the study drug

- 2) she develops a clinically significant adverse event that is ongoing and which necessitates medication or medical treatment which might affect study results
- 3) she fails to undergo the scheduled testing within the specified period of time
- 4) she has persistent non-compliance with the protocol
- 5) she does not adhere to hospital regulations

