5 out of the 10 participants recruited will be asked to be admitted to the Rockefeller University Hospital IPU 11 days earlier (2 weeks prior to Celecoxib administration) for a total of 24 inpatient days in order to determine stabilization time for fecal microbiota. 4 additional stool samples will be collected at Days 0,3, 7, and 11, +/- 1 day.

Screening Visit #1

Informed consent

Medical History and Physical exam

EKG

Waist measurement

Distribution of 3-day food diary

HIV POCT

Subjects will be instructed to fast 10 hours prior to their next visit for fasting labs.

Subjects will be instructed to discontinue taking over the counter medications (OTCs). Those subjects which require medication for relief of pain will be advised to use only Tylenol and given a week's supply.

Screening visit #2

Return of 3 day food diary

Fasting labs to include- CBC/Diff, ESR, Comprehensive Metabolic Panel, Thyroid Stimulating Hormone, lipid profile, hsCRP, PT/PTT/INR, serum estradiol

Bionutrition consult to review the 3 day food diary and determine subject's "usual diet"

A clinic meal will be provided after labs are drawn.

Dispense Tylenol 325 mg #30, 2 tablets by mouth as needed for pain.

Eligibility will be determined following lab results. Subjects will be scheduled for admission within 1-4 weeks of their screening. If greater than 1 month has passed from screening, safety labs (CBC/DIFF, CMP, PT/PTT/INR) will be re-drawn prior to admission.

Inpatient Admission

Day 0

Admit to RUH at approximately 11 AM

Study diet lunch and dinner

Day 1

Usual diet

Day 2

Spot urine for PGE-M

24 hour urine for testing of the following: PGE-M, estrogen metabolites, creatinine, volume stool sample +/- 1 day

NPO after 9 pm except water

Day 3

Fasting research labs- TNF- α , IL6, IL8, MCP-1, insulin, serum estradiol and estrogen metabolites, serum endocannabinoids

MSKCC labs: CBC, ESR, CMP, hsCRP, PT/PTT/INR, lipid panel, estradiol

Spot urine for PGE-M after completion of 24-hr urine collection

Fat biopsy

Start Celecoxib 200 mg PO BID

NPO after 9 pm except water

Day 4

Bod Pod

Continue Celecoxib 200 mg PO BID

Day 5

Usual diet

Continue Celecoxib 200 mg PO BID

Day 6

Usual diet

Continue Celecoxib 200 mg PO BID

Day 7

Usual diet

Continue Celecoxib 200 mg PO BID

Day 8

Usual diet

Continue Celecoxib 200 mg PO BID

Day 9

Usual diet

Continue Celecoxib 200 mg PO BID

Day 10

Usual diet

Continue Celecoxib 200mgPO BID

Day 11

Usual diet

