13.12 Exclusion Criteria

Please list subject exclusion criteria:

Order Number	Criteria
1	Known hypersensitivity to celecoxib, sulfonamides, aspirin, or NSAIDs
1	Known peptic ulcer disease
2	Hypertension BP > 150/90 (on 2 occasions after resting)
2	Fasting blood glucose > 165 mg/dL
3	HIV positive
3	Screening creatinine > 2X upper limit of normal
	Screening LFT results > 2x upper limit of normal

4	
5	Smokers (or stopped < 3 months ago)
11	Framingham risk score > 15
12	Evidence of active coronary disease by history and/or EKG
13	Subjects who consume 25 grams of soy protein/day or more than 45 mg of isoflavones /day, for subjects who consume this amount of soy, they may stop for 14 days prior to admission
14	Currently taking NSAIDS, aspirin, (if > once a week, stopped <30 days ago).
14	Consuming > 3 servings of fish or seafood/week
15	Currently taking fish oil, omega-3 supplements or other herbal supplements that exceed GRAS (Generally Recognized as Safe) levels, (if currently taking fish oil/omega-3 supplements, there must be a 30 day washout period)
15	current use of anti-coagulants
17	Currently taking any weight control medication
18	Currently taking thioridazine
18	Currently taking lithium
19	Currently taking any estrogen/progesterone hormones including vaginal cream, e-string, or vaginal tablets
20	Currently taking any medication that can alter fat stores as determined by the principal investigator
21	History of Inflammatory Bowel Disease or other chronic inflammatory disorders
21	History of any malignancy other than non-melanoma skin cancer in the past 5 years
22	History of any bleeding disorder
23	History of cardiovascular disease
25	Diagnosis of asthma
26	Any medical, psychological or social condition that, in the opinion of the Investigator, would jeopardize the health or well-being of the participant during any study procedures or the integrity of the data.

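### Sections 13.12 and 25.1 disagree on PT/PTT and bilirubin, so a woman can be eligible and already meet a withdrawal criterion on the same pre-drug value.

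*Combined protocol and SAP*

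**What the plan says.** **Entry (13.12).** Two laboratory exclusions bear on this point: "Screening creatinine > 2X upper limit of normal" and "Screening LFT results > 2x upper limit of normal". Bilirubin is not named, and PT/PTT has no numerical limit. The nearest criteria on coagulation are "current use of anti-coagulants" and "History of any bleeding disorder", neither of which refers to a laboratory result. A general clause excludes "Any medical, psychological or social condition that, in the opinion of the Investigator, would jeopardize the health or well-being of the participant"; it gives no laboratory threshold.

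**Withdrawal (25.1).** The laboratory items are LFT at 2 x ULN, "bilirubin 1.5-3.0 X ULN", "creatinine 2 X ULN", and PT/PTT above ULN. The LFT and creatinine items carry no comparator sign. The sentence introducing the list is permissive: subjects *may* be withdrawn. It does not say whether the values must have been taken on drug.

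**When the tests are drawn (12.7).** Screening visit 2 includes a comprehensive metabolic panel and "lipid profile, hsCRP, PT/PTT/INR, serum estradiol", and eligibility is decided once the results are in. If more than a month passes, the safety labs are repeated before admission. The metabolic panel and PT/PTT/INR are drawn again on Day 3 (Day 14 for the five women admitted early), the day of the first biopsy and the start of celecoxib. They are drawn once more on Day 13 (Day 24), the day of the last dose, the second biopsy and discharge.

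**The concern.** Entry and withdrawal limits should fit together: a value that admits a woman should not also be a listed reason to take her out. For PT/PTT and bilirubin they do not fit. Staff holding a PT slightly above ULN at screening find nothing in the 13.12 limits that excludes her, yet a criterion in 25.1 that she already meets. The protocol does not say which section governs.

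What is at stake is handling and consistency in a study of 10 women. Each has an abdominal fat biopsy on the day drug starts, and section 21.1 lists bleeding among the biopsy risks. Without a rule, two women with the same pre-drug result could be treated differently, and a woman could undergo the biopsy and begin dosing while meeting a listed withdrawal criterion.

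**Working it through.** The plan gives no figure to reproduce here. The check takes each test as a multiple of ULN and asks whether one value can both pass 13.12 and meet 25.1.

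| Test | Passes 13.12 | Meets 25.1 | Both |
|---|---|---|---|
| PT/PTT | any value (no limit) | above 1.0 | **above 1.0** |
| Bilirubin, if an LFT | up to and including 2.0 | 1.5 to 3.0 | **1.5 to 2.0** |
| Bilirubin, if not an LFT | any value (no limit) | 1.5 to 3.0 | **1.5 to 3.0** |
| Creatinine and LFT, if 25.1 means at or above 2 | up to and including 2.0 | 2.0 and above | exactly 2.0 |
| Creatinine and LFT, if 25.1 means above 2 | up to and including 2.0 | above 2.0 | none |

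**PT/PTT.** The overlap does not depend on how any sign is read. Section 13.12 has no limit and 25.1 starts at 1 x ULN.

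**Bilirubin.** Some trial values:
- 1.4 x ULN is eligible and outside the withdrawal band.
- 1.8 x ULN is eligible on either reading and inside the band.
- 2.5 x ULN is excluded if bilirubin is an LFT; otherwise it is eligible and inside the band.
- 3.5 x ULN is excluded if bilirubin is an LFT; otherwise it is eligible, and it lies above the band. As written, the bilirubin item covers 2.5 but not 3.5.

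Section 25.1 puts LFT and bilirubin on separate lines, which hints that they are distinct, but neither section says so. The documents do not list the components of the metabolic panel; I assume that bilirubin is among them.

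**Creatinine and LFT.** Both sections use 2 x ULN. Section 13.12 excludes values above 2, so 2.0 itself is eligible, and the missing sign in 25.1 leaves open whether 2.0 also meets the withdrawal item. That single point is the whole overlap.

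**Timing.** During dosing, up to the day of the last dose, the scheduled values to which 25.1 could be applied are the pre-drug ones, which is where the overlap lies. The Day 3/14 labs share a day with the biopsy and the first dose, and 12.7 does not say that their results must be seen first.

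**The case against.** The strongest case against the point is that 25.1 is discretionary and sits under a heading on toxicity, so on-drug values are the natural reading. At entry the coagulation results are in hand before eligibility is decided, anticoagulant use and bleeding disorders are excluded, and the investigator can refuse anyone under the general clause. This stands in part: meeting a criterion does not mean automatic withdrawal. But 25.1 does not restrict itself to on-drug values, and the general clause does not say how a raised PT/PTT or bilirubin should be judged.

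Three stronger readings might be inferred, and the documents do not support them.

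- *The creatinine and LFT limits contradict each other.* They are the same number, and any overlap is a single point that turns on a missing sign. That a woman just below a limit may cross it through assay variation is true of every threshold.
- *Paired data and power will be lost.* The on-drug spot and 24-hour urines begin on Day 12/23, before the only scheduled on-drug safety labs on Day 13/24, so an abnormal result there comes too late to cost the primary PGE-M pair. Sections 13.7 and 13.8 plan 15 consents for 10 evaluable women, so a woman withdrawn earlier might be replaced, although that margin must also absorb screen failures. The documents do not say how many eligible women would exceed ULN, so any probability would rest on an assumption.
- *A large on-drug rise would go unnoticed because 25.1 has no change-from-baseline term.* Section 24.6 counts abnormal laboratory findings as adverse events and has adverse events graded on a published scale. Whether a stopping criterion should refer to baseline is a clinical choice; its absence is not a contradiction between sections.

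**Conclusion.** The point holds for PT/PTT and bilirubin. Any PT/PTT above ULN, and bilirubin of 1.5 to 2.0 x ULN (or 1.5 to 3.0 if it is not an LFT), passes the listed entry limits and meets a listed withdrawal criterion. The bilirubin band also leaves values above 3.0 x ULN outside it as written. For creatinine and LFTs there is only an ambiguity at exactly 2.0 x ULN.

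The consequence is that a woman may be biopsied and start drug while already meeting a criterion in 25.1, with no stated rule for what follows. Its size is given as ranges of values, not as a number of women or a loss of power. The PT/PTT conclusion rests on the text alone. The bilirubin range depends on whether bilirubin is an LFT, but there is an overlap either way. All of it assumes that 25.1 may be applied to pre-drug values, which the text permits but does not state.

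**What to change.** Reconcile 13.12 and 25.1 so that no screening or pre-dose value both qualifies a woman and meets a withdrawal criterion. The amendment should state:

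1. how PT/PTT and bilirubin are handled at entry;
2. whether bilirubin is part of the LFTs in each section;
3. the comparator signs for LFT and creatinine in 25.1;
4. what applies above the upper end of the bilirubin band;
5. whether 25.1 applies only to values taken on drug.

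The limits themselves are for the sponsor's clinicians; none is proposed here.

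The cost is amendment wording. PT/PTT/INR and the metabolic panel are already drawn at screening, so no test is added if the panel includes bilirubin. The downside is that a few women may fail screening who would otherwise have been admitted.
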